#### **4.0 CLINICAL AND SCIENTIFIC JUSTIFICATION**

Failure of undersizing mitral annuloplasty (UMA) in patients with FMR is now an established fact. High rates of FMR recurrence after UMA have been reported in several studies, but a mechanistic basis for such failure is lacking. Due to the high rates of repair failure, these patients are receiving a mitral valve replacement (MVR), which is known to have poor durability and higher mortality. Thus, the clinical justification to understand the mechanisms underlying UMA failure is solid. The knowledge gained from this study may not directly impact these patients, but is expected to improve the treatment options available to other patients in the future.

The scientific justification for studying inter-papillary muscle separation (IPMS) as a determinant of UMA failure, stems from our previous published study. In 2014, we reported that elevated IPMS correlated with higher severity of FMR in humans. In a subsequent study in a bench model, we reported that elevated IPMS has a direct impact on valve function after UMA. Based on these two studies, we developed the hypothesis that a cut-off value for IPMS exists, which can determine who patients could have a durable repair with UMA, and which patients may require additional procedures. Based on this information, for those with higher IPMS we are proposing that papillary muscle approximation (PMA) may be a useful technique to reduce their IPMS and improve their suitability for UMA.

#### **5.0 TREATMENT OPTIONS**

Patients recruited to this study, are determined by their cardiologists to be suitable for correction of their FMR to improve their health. A transthoracic echo has been performed on them, which

[figure not shown]
depicts moderate or greater severity of FMR, and thus they were referred to us for intervention. The patients may receive mitral valve repair or mitral valve replacement, depending on their choice along with advice from the physician team. Risks and benefits of both the treatment options will be explained to the patient. If mitral valve repair is planned in these patients, they will be recruited to this study. If mitral valve replacement is planned, they will not be recruited to this study. If mitral valve repair is planned, but intra-procedurally the physician decides that mitral valve replacement is more apt, they will continue in the study. If mitral valve replacement is planned, but intra-procedurally the physician decides that mitral valve repair is more apt, they will continue in the study.

## 6.0 STRATEGIES FOR RECRUITMENT

Trial recruitment will be handled by the clinical research unit of the division of cardiothoracic surgery at Emory University. Patients will be referred to this trial from cardiology groups within Emory University, and from external cardiologists that do not have any affiliation with Emory University.

## 7.0 STUDY DESIGN

### 7.1 Schematic of study design

### 7.2 Overview of study design

This is an observational, prospective, non-randomized, clinical study to investigate the mechanistic basis for failure of undersizing mitral annuloplasty (UMA) and the efficacy of adding papillary muscle approximation (PMA) as an additional technique to UMA to improve its outcome.

**Screening:** Patients with FMR will be identified in cardiology and cardiothoracic surgery clinics at Emory Hospital, Emory St. Joseph's Hospital and Emory Midtown, and outside referral centers that refer patients to the cardiac surgery program at Emory. Existing patient medical records, including their imaging reports, will be used to identify patients with FMR. Through the duration

of this study, we will actively inform and educate our internal and external referral cardiology groups about this study, so they can refer patients to our trial. Patient medical records and imaging examinations will be used to screen for patients. Coronary angiograms that are less than 6 months old will be used to assess the cardiomyopathic process.

Informed consent: Patients that successfully clear the screening process will be approached, and provided a thorough explanation of the study purpose, procedures, risk/benefits, alternatives and follow-up schedule. If patient volunteers to participate in the study, he/she will be asked to sign one copy of an informed consent which will be copied. The original will be included in the study record, a copy will be given to the patient, and a copy scanned and uploaded to EeMR by OCR. In some cases, it is possible that some patients may undergo all the standard of care examinations before being able to be consented for the study. In such case, the patients will be consented prior to surgery, explaining to them that the study team will use their medical records and imaging information conducted prior to the consent in this study.

Release of medical information form: The patient will also sign the release of medical information form or equivalent that authorizes release of medical records, to the study investigators and sponsors.

Study recruitment: All consented patients will undergo the following standard-of-care procedures to determine their eligibility to be recruited to this study. The study team will generate a unique identification code that will identify the patient throughout the course of the study.

Following studies will be performed as standard of care procedures for patients receiving mitral valve repair, whether part of this study or not:

- Functional status assessment
- Transthoracic echocardiogram (if >6 months)
- Transesophageal echocardiogram (may use the baseline TEE in OR)
- Coronary angiogram (if >6 months)
- Medical history
- New York Heart Association Class
- Angina Class – Canadian Cardiovascular Society Classification
- Medications
- Physical examination
- Quality of life (study purposes only)
- Laboratory assessment (study purposes only)
- Cardiac MRI with gadolinium enhancement

Inclusion/Exclusion criteria:

*Inclusion criteria:*

- Mitral regurgitation of moderate or greater severity, as defined by the guidelines of the American society of echocardiography (via a transthoracic echo).
- Cardiomyopathy of ischemic or non-ischemic origins, with or without the need for coronary revascularization.
- Concomitant right sided valve repair or replacement (i.e. patients requiring concomitant tricuspid procedures).
- Age  $\geq$  18 years
- Able to sign informed consent and release of medical information forms

*Exclusion criteria*

- Any evidence of structural (chordal or leaflet) mitral lesions.
- Prior mitral valve repair
- Contraindication for cardiopulmonary bypass
- Clinical signs of cardiogenic shock at the time of randomization
- ST segment elevation myocardial infarction within 14 days prior to inclusion in this study.
- Congenital heart disease (except PFO or ASD)
- Chronic renal insufficiency defined by Creatinine  $\geq$  3.0 or chronic renal replacement therapy, who are contraindicated for cardiac surgery
- Recent history of psychiatric disease that is likely to impair compliance with the study protocol, in the judgement of the investigator
- Pregnancy at the time of randomization

**Patients will be recruited to two registries, with the procedures described as follows:**

**Registry # 1: Prospectively Identified Patients that will Receive Surgery after Recruitment and Consented to Participate in the Study**

Subjects are screened based upon medical records, external echo examinations, echo exams performed in the Emory cardiology clinics or cath labs, inclusion and exclusion criteria. Screened patients are consented and request for release of medical information is signed. Consented patients undergo battery of baseline tests that are standard of care, including transthoracic echo, transesophageal echo, and cardiac MRI. If some patients have already completed baseline tests as part of their standard of care, and are identified after these are completed, we will consent them at this stage. Patients undergo surgery, with pre-operative echo and closed chest echo. Blood draws and echocardiography will be performed at discharge and 30-days. Patients return for visits at 6 months and 1 year to undergo repeat of tests. Patients exit study after the 1st year.

If extended follow-up is determined to be necessary, patients will be re-consented at the 1-year visit.

**Registry # 2: Retrospectively identified patients, who already underwent the standard of care surgery, and were identified after the procedure is completed, and are suitable for recruitment to the study for their post-operative research**

**Rationale:** The decision to perform mitral valve surgery could be made during the surgery by the surgeon, and these patients would be suitable for this study, but would not be consented prior to their surgery. Thus, in this registry, we will identify such patients for recruitment into this study, as their first research point isn't until 6 months after their surgery.

Charts will be screened for patients who underwent surgery for the lesion of interest at Emory, who would otherwise be eligible for this study but were not recruited as it was not known if they will need mitral valve surgery. Patients who are still within 6 months ( $\pm$  1 month) after the date of their surgery will be contacted via telephone, and the study objective will be explained, verbal consent will be obtained and the date to visit Emory will be provided. Written consent will be obtained at their 6 month visit, and steps 9 and 10 described in registry # 1 will be performed.

**Registry # 3: Retrospectively identified patients, who already underwent the standard of care surgery, and were identified after the procedure is completed, and are suitable for recruitment to the study for their post-operative research.**

**Rationale:** Historical review of patients between dates 1/1/2004 to present who have undergone mitral valve surgery who were not previously identified in the study. These patients have not been consented prior to their surgery. The purpose is to increase the study sample size in order to gain statistical power for outcome analysis.

Medical charts will be screened for patients who underwent surgery between 1/1/2004 to present for the lesion of interest at Emory, who would otherwise be eligible for this study but were not recruited as it was not known if they will need mitral valve surgery or were not recruited as they may have received the surgery prior to study start date.

Study assignment: 140 patients will be recruited in total, 1) n=125 to undersizing mitral annuloplasty (UMA) and 2) n=15 to undersizing mitral annuloplasty with papillary muscle approximation (UMA+PMA). Selection will be in a non-randomized manner. Under no circumstances will more than the proposed number of patients be recruited to either groups, without prior approval from the institutional IRB and the study sponsor.

Surgical procedures:

[figure not shown]
Intra-operative echo 1: On the day of the surgery, after the patients are sedated, intubated and anesthetized, the cardiac anesthesiologist will perform a standard of care transesophageal echocardiogram.

Surgical procedures:

*Undersizing mitral annuloplasty (Figure A):* Patients undergoing this procedure will receive a commercially available annuloplasty ring of the surgeon's choice. Sutures are placed around the mitral annulus, and the metallic ring is then implanted onto the mitral annulus to reduce it in size.

*Undersizing mitral annuloplasty with papillary muscle approximation (Figure B):* Patients receiving this procedure will undergo undersizing mitral annuloplasty in a manner that is identical to the procedure outlined above. In addition to the ring implantation, one or two 4-0 pledgedet suture are used to draw the two papillary muscle tips together to reduce the IPMS.

After the procedure is complete, the patients are revived from cardiopulmonary bypass and hemodynamic stability is established.

Post-chest closure echo: Just prior to moving the patient out of the operating room, a repeat intra-operative standard-of-care echocardiogram will be performed to assess the valve function. After both procedures, the patients are revived from surgery and their post-operative care will follow established and standard of care protocols.

Follow-up time points and examinations:

*Discharge:* Following examinations will be performed before discharge:

- Transthoracic echocardiography

- Blood draw

*30-day (+/- 7 days):* Following examinations will be performed at 30-days :

- Blood draw
- Transthoracic echocardiography

*6 months post-surgery (+/- 30 days):* Following examinations will be performed at discharge at 6 months post-surgery

- Transthoracic echocardiography
- Blood draw
- Quality of life questionnaire
- HF questionnaire
- 6 minute walk test

*12 months post-surgery (+/- 90 days):* Following examinations will be performed at discharge at 6 months post-surgery

- Transthoracic echocardiography
- Cardiac MRI with contrast or transesophageal echo (whichever is possible)
- Blood draw
- QoL questionnaire
- Heart failure questionnaire
- 6MWT

Computational biomechanical modeling: Echocardiographic images, immediately after acquisition will be transferred to the core database established by the PI's laboratory. These images obtained from the patients at the different timepoints will be used for computational biomechanical modeling. The 3D echocardiographic images will be segmented and a mathematical mesh will be developed. Idealized material properties will be assigned to the mesh geometry, and the strain and stress distribution on the leaflets will be quantified under different loading conditions.

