
	
 
• Question 2: Does reducing IPMS with a papillary muscle approximation stitch reduce the FMR severity after UMA, by improving valve geometry and biomechanics. We will conduct a pilot study of 15 patients with this approach and investigate their outcomes at 1 year after the surgery.
 

Hypothesis	Elevated IPMS is a risk factor for failure of UMA and recurrence of FMR at 12 months the repair. Reducing IPMS with a papillary muscle approximation stitch can reduce FMR recurrence after UMA.
Objectives	
 
(1) Determine if pre-surgery diastolic IPMS, systolic IPMS and (diastolic-systolic) IPMS correlates with the severity of FMR at immediate post-op, 30 days, 6 months, and 12 months post-UMA.
 
(2) Does IPMS reduction with PMA performed concomitantly with UMA, help in reducing the severity of FMR at immediate post-op, 30 days, 6 months, and 12 months after surgery.
 

Primary Endpoints	The primary endpoint of this study is to investigate if pre-operative inter-papillary muscle separation (diastolic, systolic and diastolic-systolic) correlates with FMR severity at 12 months after surgery with UMA and UMA+PMA.
Secondary Endpoints	
Survival
 
 
• All-cause mortality at discharge, 6 months and 1 year
 
 
Functional Status and Hospitalizations
 
 
• MACE (death, stroke, worsening heart failure (+1 NYHA Class), CHF hospitalization, mitral valve re-intervention at 6 months and 1 year
 
• NYHA classification at 6 months and 1 year
 
• 6-minute walk test at 6 months and 1 year
 
• Readmission rates at 6 months and 1 year
 
 
Physiologic
 
Pre-operative:
 
 
• MRI 
 
- MR severity
 
- Interpapillary muscle dynamics
 
- Left ventricular function
 
- Left ventricular geometry
 
- Left ventricular perfusion and motion defects
 
- Left ventricular scar burden
 
 
 
• Echo (transthoracic and transesophageal) 
 
- MR severity (ERO and regurgitant fraction)
 
 
 

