	
Rationale: The decision to perform mitral valve surgery could be made during the surgery by the surgeon, and these patients would be suitable for this study, but would not be consented prior to their surgery. Thus, in this registry, we will identify such patients for recruitment into this study, as their first research point isn't until 6 months after their surgery.
 
Step 1) Charts will be screened for patients who underwent surgery for the lesion of interest at Emory, who would otherwise be eligible for this study but were not recruited as it was not known if they will need mitral valve surgery.
 
Step 2) Patients who are still within 6 months (<math>\pm</math> 1 month) after the date of their surgery will be contacted after surgery and the study objective will be explained, verbal consent will be obtained and the date to visit Emory will be provided.
 
Step 3) Written consent will be obtained at their 6 month visit, and steps 9 and 10 described in registry # 1 will be performed.
 
Registry # 3: Retrospectively identified patients, who already underwent the standard of care surgery, and were identified after the procedure is completed, and are suitable for recruitment to the study for their post-operative research.
 
Rationale: Historical review of patients between dates 1/1/2004 to present who have undergone mitral valve surgery who were not previously identified in the study. These patients have not been consented prior to their surgery. The purpose is to increase the study sample size in order to gain statistical power for outcome analysis.
 
Step 1) Charts will be screened for patients who underwent surgery between 1/1/2004 to present for the lesion of interest at Emory, who would otherwise be eligible for this study but were not recruited as it was not known if they will need mitral valve surgery or were not recruited as they may have received the surgery prior to study start date.

Sample size	
140 subjects in total at Emory University.
 
Group 1: 125 patients to receive UMA and followed to 12 months, with interim imaging.
 
Group 2: 15 patients to receive UMA with PMA and followed to 12 months, with interim imaging.

	
It is expected that we will recruit ~25 patients per year.
 
Group 3: patients' medical charts will be queried between 2004 – present, number of subject charts are undetermined/unknown.

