## 8.0 TIMEFRAME OF MEASUREMENTS AND DATA COLLECTION

	TTE	TEE	MRI	QOLq	HFq	6MWT	Blood
Screening	x						
Pre-op	x	X*	X*	0	0	0	0
Intra-op		x					
Chest closure		x					
Discharge	x						0
30 days	x						0

6 months	0			0	0	0	0
12 months	0	0*	0*	0	0	0	0

**x:** indicates current standard of care  
**0:** indicates non-standard of care, paid by the study  
**\***: indicates that both procedures could be performed, or only one of them, depending on what is practically possible and what the patient agrees to undergo.

**TTE:** trans-thoracic echo  
**TEE:** trans-esophageal echo  
**MRI:** magnetic resonance imaging  
**QOLq:** quality of life questionnaire  
**HFq:** heart failure questionnaire  
**6MWT:** 6-minute walk test  
**Blood:** blood collection for laboratory studies

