## 11.0 ANALYSIS PLAN

**General design issues:** This is an observational, prospective, non-randomized, single center, multiple phase study. Enrolled patients will have clinically significant FMR with either ischemic or non-ischemic cardiomyopathies. 50 patients are recruited to phase 1 (all 50 receiving undersizing mitral annuloplasty), and 90 patients to phase 2 (75 receiving undersizing mitral annuloplasty and 15 receiving undersizing mitral annuloplasty and papillary muscle approximation). In patients

receiving undersizing mitral annuloplasty, the same rigid annuloplasty ring will be used as consistently as possible, and up to two sizes of downsizing will be performed as consistently as possible. In some patients recruited to the study, the surgeon may decide to switch to mitral valve replacement, or may perform a repair and deem it to be a failure and then switch to mitral valve replacement. In either case, the patient will continue to be part of the study, but with follow-up performed only at 12 months.

**Sample size estimation and statistical analysis plan:** The primary objective of this study is to determine the correlation between pre-operative inter-papillary muscle separation and the 6 month and 12 month post-operative FMR grade after undersizing mitral annuloplasty. Pre-operative inter-papillary muscle separation will be measured and is a continuous variable, while the recurrence of FMR will be deemed binary (1: if MR greater than or equal to 2+ severity observed at 12 months; 0: if MR less than or equal to 2+ severity observed at 12 months). An ROC curve analysis will be used to determine the inflection point of inter-papillary muscle separation at which FMR will recur at 12 months after annuloplasty. Sample sizes are based on previously published data, and on ensuring the ability to detect with high probability, a clinically meaningful presumed benefit for patients undergoing mitral valve repair.

Recruitment to the papillary muscle approximation arm is not based on power analysis as it is only a pilot study.

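### If Registry 2 patients are counted from surgery, early mortality and the death part of MACE read too low; Registry 3 has no study-paid 12-month scan, and pooling it can bias recurrence risks in either direction

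*Combined protocol and SAP*

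**What the plan says.** Section 7.2 (and Study Procedures in section 1.0) defines three routes into the study.

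- **Registry 1** enrols before surgery.
- **Registry 2** covers patients whose need for mitral surgery was settled during the operation. They are found by chart screening afterwards. Those still within 6 months (± 1 month) of surgery "will be contacted via telephone, and the study objective will be explained, verbal consent will be obtained". After that, "Written consent will be obtained at their 6 month visit, and steps 9 and 10 described in registry # 1 will be performed". Steps 9 and 10 are the 6-month and 1-year visits and study exit.
- **Registry 3** is a chart review from 2004 to the present of patients "who were not previously identified in the study". Its rationale reads "The purpose is to increase the study sample size in order to gain statistical power for outcome analysis". The sample-size entry in section 1.0 lists it as Group 3, where the "number of subject charts are undetermined/unknown".

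The survival endpoint in sections 1.0 and 9.0 is "All-cause mortality at discharge, 6 months and 1 year". MACE, which includes death, is set at 6 months and 1 year.

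In the section 8.0 table, 12-month TTE, TEE and MRI all carry the code that "indicates non-standard of care, paid by the study".

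Section 11.0 defines 12-month recurrence as binary and states that "An ROC curve analysis will be used to determine the inflection point of inter-papillary muscle separation". It gives no method for mortality or MACE, no time at which a Registry 2 patient starts to be at risk, and no role for Registry 3.

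**The concern.** Two separate selection problems arise from how patients enter.

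**(a) Registry 2.** A patient who dies before the telephone call, or before the 6-month visit if written consent is what counts, cannot be enrolled. Visits and participation are timed from surgery, so the natural reading is to count mortality from surgery in everyone enrolled. Registry 2 would then add to the denominator without being able to add early deaths. Mortality, and the death part of MACE, would read too low at discharge and 6 months, and by a smaller proportion at 1 year.

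**(b) Registry 3.** The primary analysis needs an MR grade at 12 months. Registry 3 has no visit or imaging step, and the plan itself treats 12-month imaging as outside standard care. A Registry 3 patient therefore has a grade only if someone scanned for another reason, and that reason may be related to whether regurgitation came back. The stated purpose of gaining power points towards pooling, but the analysis plan is silent. If Registry 3 is pooled, both the recurrence rate and the risks quoted above and below the IPMS cut-off are exposed.

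**Working it through.** **What comes from the documents.** The group sizes agree: 125 + 15 = 140 and 50 + 90 = 140. The 12-month recurrence of 32.6% is in section 1.0. The documents give no mortality rate, Registry 2 share, scan probability or AUC, so those inputs below are assumptions.

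**(a) Mortality counted from surgery**

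Let m6 and m12 be true mortality at 6 and 12 months, and f the Registry 2 share. Assume m6 = 8% and m12 = 14%.

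*Enrolment at written consent (6-month visit):*
- 6 months: (1 − f) × m6. At f = 0.30: 0.70 × 8% = 5.6%.
- 1 year: (1 − f) × m12 + f × (m12 − m6)/(1 − m6). At f = 0.30: 0.70 × 14% + 0.30 × (6/92) = 9.8% + 2.0% = 11.8%.

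| Registry 2 share | 8% at 6 months reads | 14% at 1 year reads |
|---|---|---|
| 10% | 7.2% | 13.3% |
| 30% | 5.6% | 11.8% |
| 50% | 4.0% | 10.3% |

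*Enrolment at verbal consent, with half of the 6-month deaths before the call:* Registry 2 reads 0.04/0.96 = 4.17% at 6 months. At f = 0.30 the cohort reads 0.70 × 8% + 0.30 × 4.17% = 6.9%. The bias is smaller, with the same sign.

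*Delayed entry:* if Registry 2 joins the risk set only at enrolment, the 1-year estimate is 1 − (1 − 0.08) × (1 − 6/92) = 14%. This recovers the truth only if the two registries share the same hazard.

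*Precision:* the Wilson 95% interval for 8% is 4.5–13.7% at n = 140. With Registry 1 alone at a 30% Registry 2 share (n = 98), it is 4.1–15.1%.

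**(b) Recurrence if Registry 3 is pooled**

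Let a and b be the scan probabilities with and without recurrence, and N the number of charts, pooled with 125 protocol patients who all have a grade:

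pooled rate = (125 × 0.326 + N × 0.326a) / (125 + N × (0.326a + 0.674b))

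- a = 0.9, b = 0.5, N = 125: (40.75 + 36.68)/(125 + 78.8) = 38.0%.
- a = 0.5, b = 0.9, N = 125: (40.75 + 20.38)/(125 + 96.2) = 27.6%.
- A milder 0.8 and 0.6, N = 125: 35.2%, or 30.1% reversed.
- With 500 charts at 0.9 and 0.5: 42.6%, or 24.0% reversed. More charts make the bias larger.

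The standard error of 32.6% at n = 125 is √(0.326 × 0.674/125) = 4.2 points.

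*Risks either side of the cut-off.* Assume a binormal marker with AUC 0.70. The separation is 0.742 SD, and at the Youden cut-off of 0.371 sensitivity and specificity are both 0.645. At 32.6% recurrence, the risk is 47% above and 21% below. At 38.0% it is 53% and 25%; at 27.6% it is 41% and 17%.

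*AUC and the cut-off itself.* If scanning depends on recurrence only, the IPMS distribution within each outcome group is unchanged, so neither moves. If scanning depends on IPMS (0.9 above the cut-off, 0.5 below, 125 charts), the cut-off moves by 0.09 SD, against a sampling SD of about 0.39 at n = 125. With a steeper 0.9 and 0.2 and 500 charts, about 125 + 500 × (0.450 × 0.9 + 0.550 × 0.2) = 382 patients have a grade. The cut-off then moves by about 0.34 SD, against a simulated sampling SD of about 0.28. The size depends wholly on the assumed pattern.

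**The case against.** Several counter-arguments have force.

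- **Nothing says everyone is counted from surgery.** True. The plan states no time origin for survival, so (a) is conditional on that choice. Nothing rules it out either, and the visit timing makes it the likely default.
- **Only secondary endpoints are affected, and no mortality test is planned.** This stands. A reader might infer that Registry 2 also distorts the primary 12-month result through survivorship. The documents do not support that: the analysis needs a 12-month grade, so it is limited to survivors in Registry 1 as well. Non-fatal MACE events before enrolment could also be recovered from charts in patients who lived.
- **The bias is inside the confidence interval.** At shares of 10–30% the 6-month figures (7.2% and 5.6%) lie within 4.5–13.7%. But the error in (a) runs one way, the interval does not reflect it, and it is avoidable.
- **Registry 3 would pick up the missing deaths.** It runs to the present with overlapping eligibility, but excludes patients already identified, so the destination of someone found in Registry 2 screening who had died is not stated. Adding such deaths to Registry 2 survivors would not repair the estimate: living candidates who decline or cannot be reached would be in neither group. At a true 8%, with 90/80/70% of survivors enrolled (assumed), 0.08/(0.08 + 0.92 × share enrolled) gives 8.8/9.8/11.0%. Nor can Registry 3 deaths be taken as complete: it reads charts only, and section 6.0 says patients also come from outside cardiologists.
- **Registry 3 is already apart from the 140.** Correct. Section 1.0 lists Group 3 separately, so its relation to the 140 is not in doubt. What is open is whether it enters the outcome analysis.

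**Conclusion.** The point holds in this limited form and should be addressed.

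For (a), the direction follows from the consent timing, given counting from surgery. The size is unknown: with written consent as entry, the proportional shortfall at 6 months equals the Registry 2 share, and it is smaller at 1 year or if verbal consent is entry. The illustration of 8% reading 5.6% (6.9% on the verbal-consent assumption) rests on assumed mortality and an assumed 30% share.

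For (b), the direction is not known. Pooling can move recurrence up or down by about 5 points under the 0.9 and 0.5 assumption with 125 charts, a little more than one standard error, and by less under milder assumptions.

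It would be tempting to conclude that Registry 3 invalidates the IPMS cut-off, or conversely that any shift is always below sampling error. Neither follows. AUC and cut-off are untouched if scanning depends on recurrence alone; otherwise the shift depends on a pattern that the documents do not describe.

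**What to change.** Add to section 11.0:

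1. **Mortality and MACE.** Estimate events up to 6 months in patients enrolled before surgery (Registry 1), noting that this describes planned mitral surgery. In any time-to-event analysis that includes Registry 2, use delayed entry at the enrolment date, say whether that is verbal or written consent, and state the assumption of similar hazards in the two registries. Do not combine Registry 2 survivors with deaths found by chart review unless the denominator is all screened eligible patients.
2. **Primary IPMS analysis.** Base it on Registry 1 and 2 patients with a measurable pre-operative IPMS and a protocol 12-month assessment. Report deaths before 12 months and missing 12-month grades by registry. Add a best/worst-case analysis for unscanned survivors; for example, an observed 32.6% with 20% unscanned gives bounds of 0.8 × 32.6% = 26.1% and 26.1% + 20% = 46.1%.
3. **Registry 3.** Use it only as a separate supportive analysis, report the proportion scanned, and do not assume that its deaths are complete. Reword the power rationale in sections 1.0 and 7.2.
4. **Editorial.** Section 7.2 announces two registries and then describes three, as section 1.0 does. Correct the count.

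No new visits or tests are needed. The costs are early-event estimates on fewer patients (at a 30% Registry 2 share, the interval for 8% widens to the n = 98 figure above) and the loss of the nominal power gain from Registry 3.
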